### 2.3 EXPLORATORY OBJECTIVES

Exploratory objectives may include:

- Assessment of the baseline humoral immunity to poliovirus type 2 as neutralizing antibodies in infants at approximately 6 weeks of age before any vaccination with either bOPV or IPV.
- Assessment of the priming by bOPV+IPV of immune responses to a single dose of both nOPV2 candidates (all lots) at  $10^5$  and  $10^6$  CCID50 dose levels in infants at approximately 18–22 weeks of age relative to a control sample of infants receiving the same vaccination schedule followed by one or two doses of Sabin mOPV2 in a prior study (M2) designed to serve as a control for the current study.
- Investigation of the extent of viral shedding following the administration of two  $10^6$  CCID50 doses of nOPV2 candidates (all lots) in healthy children aged 1 to 5 years and of  $10^5$  CCID50 doses of nOPV2 candidates (all lots) in infants at approximately 18–22 weeks of age.
- Assessment of the genetic sequence heterogeneity and stability of virus isolated from a subset of stool samples of participants following one or two doses of the nOPV2 candidates (2018 lots) at  $10^6$  CCID50 dose level in 1 to 5 year-olds, and at  $10^5$  and  $10^6$  CCID50 dose levels, in infants at approximately 18–22 weeks of age

after having been previously vaccinated with 3 doses of bOPV and 1 dose of IPV, and contrast this heterogeneity profile with a control sample of participants receiving the same vaccination schedule followed by **one or two doses** of Sabin mOPV2 in a prior study designed to serve as a control for the current study. **A similar exploratory assessment of genetic stability of samples from 1 to 5 year-olds and infants in Stage I administered with nOPV2 candidate 2 [2016] may be performed.**

- Assessment of the immune response to parallel routine vaccinations through assessment of antibodies to hepatitis B (HBV) and *Haemophilus influenzae* type b (Hib) vaccine components after a full infant primary series and contrast these values with those in participants in a prior study (M2) designed to serve as a control for the current study.

### **3. STUDY ENDPOINTS**

#### **3.1 PRIMARY ENDPOINTS**

The following endpoints will be evaluated by group and overall:

- Safety: incidence of Serious Adverse Reactions (SAR), severe AR and IMR, i.e. SAEs, severe AEs (grade 3), or IMEs considered consistent with a causal association with study vaccines as of the informed consent signature date and throughout the study period in all groups.
- Immunogenicity: seroprotection rate of type 2 polio neutralizing antibodies at Day 28 following a single  $10^5$  or  $10^6$  CCID50 dose of nOPV2 candidates in all groups. Seroprotection rate is defined as the percentage of subjects with type 2-specific antibody titers  $\geq 1:8$  per group.

#### **3.2 SECONDARY ENDPOINTS**

The following safety and immunogenicity endpoints will be evaluated by time-point, group and overall.

Safety:

- Incidence of any SAEs, of any AEs grade 3, and of any IMEs as of the informed consent signature date and throughout the study period **in all groups**. (The following will be considered IMEs: medically significant events that do not meet any of the SAE criteria [see Section 11.1.3], but may require medical or surgical consultation or intervention to prevent one of the other serious outcomes listed in the SAE definition).
- Incidence of any mild and moderate solicited AEs (fever, vomiting, abnormal crying, drowsiness, loss of appetite and irritability) for 7 days after the first dose in all groups and for 7 days after the second dose in all groups **receiving two doses**.
- Incidence of any mild and moderate unsolicited AEs throughout the study period by causal association with study vaccines.

- Incidence and description of deviations from normal clinical laboratory assessments at Day 0 and 28 days after first dose of nOPV2 in all groups, Day 7 after the first dose of nOPV2 candidates in **all groups**, and at 28 days after the second dose of nOPV2 candidates in all groups receiving two doses.

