- g. Group B1L1[2018] receive  $10^5$  CCID50 candidate 1 (2018); Group B2L1[2016] receive  $10^5$  CCID50 candidate 2 (2016); Group B2L1[2018] receive  $10^5$  CCID50 candidate 2 (2018); Group B1H1[2018] receive  $10^6$  CCID50 candidate 1 (2018); Group B2H1[2016] receive  $10^6$  CCID50 candidate 2 (2016); Group B2H1[2018] receive  $10^6$  CCID50 candidate 2 (2018).
- h. Parents/guardians will be asked to collect if available the first stool every day in the provided receptacle and bring the samples with them at the next scheduled visit. After each vaccine dose, daily collection on Days 0 (before vaccination) to 10 plus collection on Days 14, 21 and 28. It will be acceptable to collect stool samples at day 14 (-1 or +2 days) and at days, 21, 28, 42, 49 and 56 using the same time windows for the corresponding study visit.
- i. Solicited AEs will be collected for Days 0-7 using electronic diaries.
- j. Daily remote contact (phone call or text message) from Day 0 to Day 14 and also on Day 21 after the first vaccine dose.
- k. Serious Adverse Events and intake of concomitant medication(s) will be monitored continuously from informed consent signature date until the last study-related activity. Parents/guardians can record unsolicited AEs on their child's diary card.
- l. Parents will be asked about any Serious Adverse Events or Important Medical Events since the last visit.

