## **6. VACCINES**

Study vaccines: novel monovalent OPV type 2 (nOPV2) candidates 1 and 2 are produced by Bio Farma, Indonesia. Lots used will be nOPV2 candidate 2 (lot 2016), **nOPV2 candidate 1 (lot 2018) and nOPV2 candidate 2 (lot 2018)**.

Other vaccines: licensed bOPV and IPV for pre-vaccination of subjects in infant cohorts B prior to administration of the study vaccine. DTPw-HB-Hib will be provided by the sponsor. Pneumococcal conjugate and Rotavirus vaccines will be provided by the local National Immunization Program.

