#### **10.1.1 Study Populations**

The following populations will be considered for analysis:

- Total Vaccinated population, defined as all subjects who received at least one dose of study vaccine.
- Per-Protocol (PP) population, consisting of all eligible study participants who are in the Total Vaccinated population and who receive all of the immunizations scheduled for the group to which they are allocated and excludes those subjects who received any therapy that could significantly affect the subject's immune status and those subjects who meet criteria outlined in Section 5.3. The per-protocol population will be adapted by time point to allow subjects to contribute data to per-protocol analyses until such time as they become disqualified. All deviations and violations occurring in the study will be reviewed prior to database lock and classified as either minor or major.

Unless specified otherwise, the Total Vaccinated population will be used for safety/tolerability analysis and analysis of demographics. Immunogenicity and viral shedding analyses will be primarily conducted in the per-protocol population.

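### In infants, the all-cause SAE, grade 3 AE and IME incidences count from consent at Day -84, so they include about 12 weeks before allocation and the first nOPV2 dose

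*Combined protocol and SAP*

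**What the plan says.** The first safety bullet of Section 3.2 (and its Synopsis counterpart) takes the incidence of any SAE, any grade 3 AE and any IME "as of the informed consent signature date and throughout the study period". It has no causality condition. The Section 3.2 endpoints "will be evaluated by time-point, group and overall".

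The primary safety endpoint in Section 3.1 has the same start date but a filter: it takes only events "considered consistent with a causal association with study vaccines as of the informed consent signature date and throughout the study period in all groups". Section 6 identifies the "Study vaccines: novel monovalent OPV type 2 (nOPV2) candidates 1 and 2" and lists bOPV and IPV under other vaccines.

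Both infant Time and Events Schedules place consent at Day -84, routine vaccination visits at Days -84, -56 and -28, and randomisation and the first nOPV2 dose at Day 0.

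The documents disagree on what is collected before Day 0:
- The adverse-event row of both infant schedules is marked only from Day 0.
- The footnote to that row says "Serious Adverse Events and intake of concomitant medication(s) will be monitored continuously from informed consent signature date until the last study-related activity".
- Sections 8.1 and 8.5.1 start collection of all AEs at consent.

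Safety is analysed in the "Total Vaccinated population, defined as all subjects who received at least one dose of study vaccine" (Section 10.1.1). This restricts which infants are analysed, not which event dates count. Section 10.1.2 limits the Stage II interim safety endpoints to 28 days after each vaccination, then adds a final-report table of unsolicited events over the whole study period.

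**The concern.** All-cause incidence is the check on the causality judgement that defines the primary safety endpoint. It should describe what happened after nOPV2. In infants, the rule as written attributes to each nOPV2 group the events that followed bOPV, IPV, DTPw-HB-Hib, pneumococcal and rotavirus vaccination, before any infant had been allocated.

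Section 2.2 contrasts this all-cause safety with M2. If both studies count a similar pre-dose period, the shared background pulls the contrast toward no difference. If they count different periods, the contrast partly reflects the counting rule. The documents do not give M2's counting window.

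The numerator and denominator also do not match. An infant who leaves during the routine series is outside the Total Vaccinated population, while pre-dose events in infants who continue are counted. The pre-dose part of the incidence therefore describes only those who reached Day 0.

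**Working it through.** **Inputs.** Pre-dose period 84 days (Day -84 to Day 0, infant schedules). Last follow-up contact at Day 180 (one dose) or Day 208 (two doses). Under Sections 8.1 and 8.5.1, all AEs are collected to 28 days after the last vaccination, i.e. Day 28 or Day 56, and SAEs and IMEs to six months.

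**The plan's own figure.** The Synopsis gives infant study durations of about 9 months (one dose) and 10 months (two doses). With 30.44 days per month:
- From consent: (84 + 180)/30.44 = 8.7 months; (84 + 208)/30.44 = 9.6 months.
- From first nOPV2 dose: 180/30.44 = 5.9 months; 208/30.44 = 6.8 months.

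Only the count from consent matches, so the plan's study period does include the 84 pre-dose days.

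**Pre-dose share of the counting window** = pre-dose days / (pre-dose days + post-dose days). The last column shows an assumed pre-dose period of 70 to 98 days, to allow for visit windows.

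| Events | Group | Share at 84 days | Share at 70–98 days |
|---|---|---|---|
| SAE/IME | one dose | 84/264 = 32% | 28–35% |
| SAE/IME | two doses | 84/292 = 29% | 25–32% |
| Grade 3 AE, if collected from consent | one dose | 84/112 = 75% | 71–78% |
| Grade 3 AE, if collected from consent | two doses | 84/140 = 60% | 56–64% |

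A share of the window equals a share of events only at a constant event rate. The grade 3 rows also require the collection start in 8.5.1. If the schedule row governs, non-serious grade 3 AEs before Day 0 would not be systematically collected.

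**What this does to a contrast (illustration).** The background rates are assumed, and both arms are assumed to be counted from consent. Let r be the 180-day background SAE incidence and h = -ln(1 - r)/180. For one-dose infants:
- Background incidence from consent: 1 - exp(-264h).
- With a doubled post-dose hazard: 1 - exp(-(84 + 2×180)h) = 1 - exp(-444h).
- Risk ratio when counting from first dose: (1 - exp(-360h))/r.

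At r = 5%, h = 0.000285. Background incidence rises from 5% to 7.25%, or from 8.1 to 11.7 expected infants in a group of 162. The doubled hazard gives 11.9% from consent, a risk ratio of 1.64. From first dose it gives 9.75%, a risk ratio of 1.95. Over r = 2% to 10%, the ratio is 1.60–1.67 from consent against 1.90–1.98 from first dose.

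For grade 3 AEs collected from consent, with a 28-day background of 1% to 5% and the same method (112 days against 28), a doubling would show as 1.22–1.24 instead of 1.95–1.99.

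**If the windows differ.** If M2 were counted only from its study dose, r = 5% and no true difference would give 7.25%/5% = 1.45 against nOPV2. The direction therefore depends on a rule that the documents do not state for M2.

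**The case against.** The strongest reply is that the plan already separates post-dose events where it matters.

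- **Primary endpoint.** A reader might infer that the primary safety endpoint is contaminated too. The documents do not support that. It needs a causal association with study vaccines, which Section 6 identifies as nOPV2, and an event before the first dose cannot meet that. Sections 10.1.6 and 11.3 do use looser words (immunization, the vaccination) when defining a serious adverse reaction, although 11.3 opens by asking about the investigational vaccine. The endpoint is largely, not perfectly, protected.
- **Other endpoints.** Solicited AEs cover the 7 days after each nOPV2 dose, and laboratory endpoints start at Day 0. This stands.
- **Interim comparison with M2.** The Stage II interim report makes the formal M2 comparisons on 28-day windows, and Sections 3.2 and 10.1.6 also require summaries by time-point. This narrows the point without closing it. Both sections also ask for an overall summary, and the final report adds an all-events table. Neither 10.1.2 nor 10.1.6 says that the vaccination starting a 28-day window is nOPV2. Routine visits are nominally 28 days apart, so windows opened by routine doses would cover the whole 84 days.
- **AE definition.** Section 11.1.1 sends conditions already present before the study vaccination to medical history. That removes some pre-dose events, but the same section keeps pre-treatment events caused by protocol procedures, and Section 3.2 still starts at consent.
- **Grade 3 figure.** Taking 75% as the expected share would be too strong, because the infant schedules mark no AE assessment, diary or remote contact before Day 0. It is an upper case.
- **Consequence.** Safety is analysed descriptively with no margin, and DSMB age and dose steps use 14-day post-dose data. A reader might also infer bias between the two 2018 candidates. Pre-dose events precede their randomisation within dose level, so they add noise only. Low and high dose are randomised separately, so that argument does not extend to dose contrasts.
- **Denominator.** Leaving infants who never received nOPV2 out of the Total Vaccinated population is appropriate. The mismatch arises from the numerator's start date.

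**Conclusion.** The point holds for one secondary endpoint in infants (any SAE, any grade 3 AE, any IME, in its overall form) and for the final all-events table. Following the plan literally puts pre-exposure events into the nOPV2 group incidences. The size is 29–32% of counted SAEs/IMEs at a constant rate. For grade 3 AEs it is up to 60–75%, conditional on collection from consent, which the documents leave unresolved.

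The effect on the M2 contrast is dilution if M2 is counted alike, and is otherwise not predictable from these documents. Cohort A is less affected, since consent is at most 4 weeks before Visit 1. The point does not undermine the primary safety endpoint or the DSMB steps. It does not undermine the interim 28-day comparisons either, provided vaccination there means nOPV2. The change should be made before database lock, because the plan states its counting rule and a silent split at Day 0 would depart from it.

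**What to change.** 1. In Sections 3.2 and 10.1.6 (and the matching Synopsis text), define the all-cause SAE, grade 3 AE and IME group incidences as events with onset on or after the first nOPV2 dose.
2. In Sections 10.1.2 and 10.1.6, state that the vaccination opening each 28-day window is an nOPV2 dose.
3. Tabulate events from consent to Day 0 separately, for all enrolled infants whether or not they went on to nOPV2.
4. Apply the same windows to the M2 data, and report it if M2's collection does not allow this.
5. Reconcile the adverse-event row of both infant schedules with its footnotes and with Sections 8.1 and 8.5.1, so that it is clear which events are collected before Day 0.

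The cost is protocol and SAP wording and one extra table. No new visits or data are needed.

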#### Immunogenicity:

- Median and geometric mean antibody titers of type 2 polio neutralizing antibodies at Day 0 and at 28 days after the first dose of nOPV2 in all groups, and 28 days after the second dose of nOPV2 in **all groups receiving two doses**.
- Seroconversion rate at Day 28, 28 days after the first dose of nOPV2 in all groups, and **at Day 56**, 28 days after the second dose of nOPV2 in all groups receiving two doses. Seroconversion is defined as a change from seronegative to seropositive, or in seropositive subjects as an antibody titer increase of  $\geq 4$  fold over Day 0 titer corrected for maternal antibody titers where applicable/age-appropriate.
- Seroprotection rate of type 2 polio neutralizing antibodies at Day 0 in all groups, at 28 days after the first dose of nOPV2 **in all 1 to 5 year-old groups, and at Day 56**, 28 days after the second dose of nOPV2 in **all 1 to 5 year-old groups and two-dose infant groups**.

#### Shedding of poliovirus

- Descriptive analysis of viral shedding as determined using **RT-PCR** (viral identity) and 50% cell culture infective dose (CCID50; titer) after viral extraction from a subset of stool samples taken at fixed time points following the first dose from **all 1 to 5 year-old groups and all infant groups** administered the 10^6 CCID50 dose.
- Potential for neurovirulence (as measured in an animal model) of shed virus extracted from a subset of stool samples following the first dose from **both 1 to 5 year-old groups and both infant groups** administered the 10^6 CCID50 dose of **each of the 2018 lots of nOPV2 candidates 1 and 2**, respectively.

### 3.3 EXPLORATORY ENDPOINTS:

- Median and geometric mean antibody titers of type 2 polio neutralizing antibodies in infants at 6 weeks of age (Day -84) before receiving their first bOPV vaccination to provide a measure of maternal antibodies.
- Descriptive and exploratory analysis of 1 to 5 year-olds and 18–22 week-old infants developing a polio type 2 seroconversion within 1 week of nOPV2 exposure, i.e. 7 days after their first dose of nOPV2.
- Descriptive analysis of viral shedding **following a second dose** in 1 to 5 year-olds, and infant groups administered **two 10^6 CCID50 doses** of each nOPV2 candidate.
- **Descriptive analysis of viral shedding in all infant groups administered one 10^5 CCID50 dose of each nOPV2 candidate.**

- Descriptive analysis of viral shedding in all infant groups administered two  $10^5$  CCID50 doses of each nOPV2 candidate.
- Exploratory endpoints may also include assessment of the genetic stability of shed virus at one or more time points following two doses  $10^6$  CCID50 of each nOPV2 candidate, following one dose of candidate 2 (2016), or one or two  $10^5$  CCID50 doses of all nOPV2 candidates.
- Exploratory endpoints may also include assessment of the potential for neurovirulence of shed virus at one or more time points following two  $10^6$  CCID50 doses of nOPV2 candidates, following one dose of candidate 2 (2016), or one or two  $10^5$  CCID50 doses of nOPV2 candidates.
- Assessment of antibody levels and proportions displaying protective levels against HBV antigen ( $\geq 10$  mIU/mL) and PRP antigen ( $\geq 0.15$   $\mu$ g/mL) in all infant groups 4 weeks after the last dose of DTPw-HBV-Hib (coincides with Day 0 serum sample for polio antibodies).

## 4. STUDY DESIGN

### 4.1 OVERVIEW OF STUDY DESIGN

This will be a single center, age de-escalation, partly-randomized study in cohorts of healthy children aged 1 to 5 years (cohort A) and bOPV-IPV vaccinated healthy infants from age 6 weeks (cohort B), performed in two consecutive stages as follows:

#### Stage I

- **Group A2H2[2016]:** 50 IPV and/or OPV vaccinated participants aged 1 to 5 years administered two  $10^6$  CCID50 doses of candidate 2 (2016), separated by 28 days.

Age de-escalation will be based on general safety data (solicited and unsolicited AEs and clinically significant abnormal laboratory values) through 14 days post dose 1 in 1 to 5 year-olds presented to the DSMB. After the DSMB recommendation to proceed, the younger cohort will be randomized to the following groups:

- **Group B2L1[2016]:** 162 infants enrolled at 6 weeks of age (-7 to +14 days) vaccinated with 3 doses of bOPV at 6, 10 and 14 weeks of age and 1 dose of IPV at 14 weeks of age, followed at 18–22 weeks of age with one  $10^5$  CCID50 dose of candidate 2 (2016).
  - o **Group B2L2[2016]:** a sub-group of 50 infants will be randomly selected from B2L1[2016] to receive a second  $10^5$  CCID50 dose of candidate 2 (2016), 28 days later.

Following completion of post-dose 1 safety assessment from the first 50 subjects from group B2L1[2016] and after the DSMB recommends to proceed, infants will be randomized to groups B2H1[2016] and B2H2[2016]. Dose escalation will be based on general safety data (solicited and unsolicited AEs and clinically significant abnormal laboratory values) through 14 days post dose 1 in first 50 subjects from group B2L1[2016].

- **Group B2H1[2016]:** 162 infants enrolled at 6 weeks of age (-7 to +14 days) vaccinated with 3 doses of bOPV at 6, 10 and 14 weeks of age and 1 dose of IPV at 14 weeks of age, followed at 18–22 weeks of age with one  $10^6$  CCID50 dose of candidate 2 (2016).
  - o **Group B2H2[2016]:** a sub-group of 50 infants will be randomly selected from B2H1[2016] to receive a second  $10^6$  CCID50 dose of candidate 2 (2016), 28 days later.

---

#### Stage II

Stage II will be performed following completion in Stage I of the enrollment and a minimum of 14 days safety follow-up in at least 50 subjects of group B2H2 after administration of  $10^6$  CCID50 nOPV2 candidate 2 [2016], and with the recommendation of the DSMB. In Stage II the process will be repeated in the same fashion as in Stage I, subject to any programmatic changes necessitated by observations in Stage I, with randomized enrollment to candidate within age group and dose level. Enrollment of

subjects for Stage II may begin before the above-defined completion threshold but no administrations of nOPV2 are to be performed before this threshold is achieved.

Following completion of Stage I, with administration of nOPV2 candidate 2 (2016), with the agreement of the DSMB and when the 2018 lots of nOPV2 candidates 1 and 2 are available, the process will be repeated in the same fashion in Stage II with new cohorts of 1–5 year old children and 18–22 week-old infants randomly allocated to receive either nOPV2 candidate 1 or nOPV2 candidate 2 (2018 lots) in the following groups:

- **Group A1H2[2018]:** 50 IPV and/or OPV vaccinated participants aged 1 to 5 years administered with two  $10^6$  CCID50 doses of candidate 1 (2018) separated by 28 days.
- **Group A2H2[2018]:** 50 IPV and/or OPV vaccinated participants aged 1 to 5 years administered with two  $10^6$  CCID50 doses of candidate 2 (2018) separated by 28 days.

Age de-escalation will be based on general safety data (solicited and unsolicited AEs and clinically significant abnormal laboratory values) through 14 days post dose 1 in 1 to 5 year-olds presented to the DSMB. After the DSMB recommendation to proceed, the younger cohort will be enrolled and randomized to the following groups:

- **Group B1L1[2018]:** 162 infants enrolled at 6 weeks of age (-7 to +14 days) administered with 3 doses of bOPV at 6, 10 and 14 weeks of age and 1 dose of IPV at 14 weeks of age, followed at 18–22 weeks of age with one  $10^5$  CCID50 dose of candidate 1 (2018).
  - **Group B1L2[2018]:** a sub-group of 50 infants will be randomly selected to receive a second  $10^5$  CCID50 dose of candidate 1 (2018), 28 days later.

Following completion of post-dose 1 safety assessment from the first fifty subjects from each group B1L1(2018) and after the DSMB recommends to proceed, infants will be randomized to groups B1H1(2018), B1H2(2018). Dose escalation will be based on general safety data (solicited and unsolicited AEs and clinically significant abnormal laboratory values) through 14 days post-dose 1 in group B1L1(2018).

- **Group B1H1[2018]:** 162 infants enrolled at 6 weeks of age (-7 to +14 days) vaccinated with 3 doses of bOPV at 6, 10 and 14 weeks of age and 1 dose of IPV at 14 weeks of age, followed at 18–22 weeks of age with one  $10^6$  CCID50 dose of candidate 1.
  - **Group B1H2[2018]:** a sub-group of 50 infants will receive a second  $10^6$  CCID50 dose of candidate 1, 28 days later.

